Chief Investigator:

Signature: Date: 21/NOV/2024

Print Name (in full): [name].....

Position: Doctoral Research Fellow.....

On behalf of the Study Sponsor:

Signature: Date: 07/11/2024

Print Name (in full): [name]

Position: RM&G MANAGER- UCLH& UCL JRO

STUDY SUMMARY

IDENTIFIERS	
IRAS Number	330315
REC Reference No.	24/EM/0282
Sponsor Reference No.	174194
Other research reference number(s)	UCL Data Protection: Z6364106/2023/09/15 ClinicalTrials.gov registration *insert*
Full (Scientific) title	STI Prophylaxis and Emergence of Antimicrobial Resistance
Health condition(s) or problem(s) studied	Antibiotic prophylaxis for bacterial sexually transmitted infections; antimicrobial resistance; gut and throat microbiomes
Study Type	Observational
Target sample size	108
STUDY TIMELINES	
Study Duration/length	28 months
Expected Start Date	January 2025
End of Study date	April 2027
Key Study milestones	03/2023 Funding awarded (British Infection Association) 08/2023 Funding awarded (British HIV Association) 05/2024 Funding awarded (NIHR) 01/2025 Aim for REC approval; Study site setup 01/2025 Recruit first participant 07/2025 Recruit final participant 07/2026 Final participant final follow-up visit 04/2027 NIHR funding ends; Complete study
FUNDING & OTHER	
Funding	National Institute for Health and Care Research (NIHR) Doctoral Fellowship £589,590 (NIHR303717); British Infection Association (BIA) £10,000 (2023/[name]); British HIV Association (BHIVA) £9,979.96 (BHIVA/5020/2023/[name])
STORAGE of SAMPLES / DATA (if applicable)	
Human tissue samples	Stool samples and oropharyngeal swabs. Collected and temporarily stored at the study site (Central and North West London NHS Foundation Trust). Study samples transferred to collaborating institution for processing and storage (Department of Biology, University of Oxford, [name]). Samples and extracted bacterial DNA will be stored at the Department of Biology, University of Oxford) for the duration of the study.
Data collected / Storage	Pseudonymised questionnaire responses will be stored at UCL
KEY STUDY CONTACTS	
Chief Investigator / Principal Investigator	[name] Email: [contact] , [contact] [contact]
Clinical Project Manager	[name]

	Email: [contact] [contact]

1 INTRODUCTION

STI prophylaxis is the use of antibiotics before sex (pre-exposure-prophylaxis, or PrEP) or after sex (post-exposure prophylaxis, or PEP) to prevent acquisition of bacterial sexually transmitted infections (STIs). There is growing evidence that men who have sex with men (MSM), particularly MSM using HIV-PrEP or living with HIV, are buying antibiotics online to take as STI prophylaxis.[1,2] This is not currently endorsed by the British Association for Sexual Health and HIV (BASHH) or UK Health Security Agency (UKHSA), citing concerns about antimicrobial resistance (AMR) although new guidelines are in preparation and will likely recommend STI prophylaxis for some patient groups.[1] Recent trials demonstrated efficacy of doxycycline-PEP (commonly called 'DoxoPEP') in preventing chlamydia, syphilis, and gonorrhoea.[3,4] There is a need to understand the AMR risks to inform UK clinical guidance and STI prophylaxis implementation. Among MSM, high incidence of antibiotic resistant infections, altered microbiomes linked to sexual behaviours and living with HIV, and dense overlapping sexual networks, raise concerns about the possible impact of long-term antibiotic use. This study will develop the methodology needed to evaluate AMR emergence and microbiome changes in MSM who are using STI prophylaxis through bacterial genomics. These data will also inform further research on STI prophylaxis, AMR epidemiology, and microbiomes and subsequently clinical and public health decisions on STI prophylaxis.

2 BACKGROUND AND RATIONALE

Rates of bacterial STIs have been rising for the last decade and MSM are disproportionately impacted by STIs, particularly antibiotic resistant STIs. [5,6] This poses a serious public health threat and represents an increased burden on NHS sexual health services (SHS). Novel approaches are needed to halt and reverse these trends. HIV-PrEP provides an established, safe, and effective model for biomedical interventions to prevent STIs. There is growing interest in STI prophylaxis with small but significant numbers self-sourcing antibiotics, and very high levels of acceptability (up to 84%) among MSM if shown to be safe and effective.[7,8,9] There are concerns about the risk of AMR development in commensal and bystander organisms, as well as the impact on gut and other microbiomes. A debate is ongoing in the UK and elsewhere on the introduction of doxycycline-PEP for populations with high STI incidence where evidence of efficacy exists.[10,11] As MSM continue to self-source antibiotics for STI prophylaxis, and implementation by the NHS in the UK is planned – robust AMR and microbiome outcome data will be necessary to understand the risks and inform surveillance.

Efficacy of doxycycline prophylaxis

In 2022, the DOXYPEP randomised controlled trial (RCT) from the USA provided strong evidence for the efficacy of doxycycline-PEP to reduce bacterial STI incidence when taken within 72 hours of condomless sexual contact.[4] The study found a 65% reduction in STI incidence per quarter (RR0.35 (95%CI 0.27-0.46)), with significant reductions in gonorrhoea (*Neisseria gonorrhoeae*), chlamydia (*Chlamydia trachomatis*) and syphilis (*Treponema pallidum*) incidence among MSM and transgender women (TGW) on HIV-PrEP or living with HIV.[4] At study baseline tetracycline resistance among *N.gonorrhoeae* isolates was 20%, which limits generalisability to the UK where it is significantly higher (62%).[12] The French SPEAR, EDGE (Sponsor) number 174194, IRAS 330315, Protocol, 1.1, 16/DEC/2024

DOXYVAC study of doxycycline-PEP and meningococcal B vaccine found significant reductions in chlamydia or syphilis (aHR0.17 (0.12-0.26)) and gonorrhoea (aHR0.67 (0.52-0.87)) with doxycycline-PEP.[4] Smaller RCTs from the USA, France and Canada also demonstrated efficacy of doxycycline-PEP and daily doxycycline-PrEP in reducing incidence of chlamydia and syphilis in MSM.[13-15] In 2023, a modelling study examined different doxycycline-PEP strategies, such as targeting all MSM/TGW, HIV-PrEP users, or only people with multiple STIs diagnosed.[16] Use of doxycycline-PEP in individuals with concurrent or repeated STIs could substantially reduce subsequent STIs.[16] However, an RCT in Kenya in cisgender women found doxycycline-PEP did not reduce incident bacterial STIs, which the study investigators believed to be adherence related.[17]

Use and acceptability

Surveys from the UK, Netherlands, and Australia estimate STI prophylaxis use among MSM using HIV-PrEP or living with HIV to be 3%-10%. [2,7,18] There was also very high levels of acceptability of STI prophylaxis among MSM (up to 84%). [8,9] Of concern is that up to 40% of STI prophylaxis users report using non-doxycycline antibiotics, such as azithromycin. [2] In recent survey by CNWL and UCL, we found that STI prophylaxis users continued to use non-doxycycline antibiotics, despite increased awareness and discussion about 'doxycycline-PEP' ([name], [name] and [name], unpublished). 80% of respondents (n=440) in this survey were 'somewhat' or 'very likely' to use doxycycline-PEP/PrEP if deemed safe and effective.

AMR

There are concerns about further development of AMR in MSM sexual networks that already have high rates of STIs with AMR. [12] Unregulated use of self-sourced antibiotics is a particular concern. Doxycycline (a tetracycline antibiotic) is needed as first-line treatment for STIs such as chlamydia, syphilis, and *Mycoplasma genitalium*, as well as respiratory, skin, and other infections. Overall, data on AMR associated with doxycycline prophylaxis from trials remains very limited, or focuses on specific organisms (*Staphylococcus aureus*, *Escherichia coli*, and *Neisseria* species); with no clear conclusions on AMR or the impact long-term doxycycline-PEP has on human microbiomes, although further analyses are expected. [3,4,15] In DOXYPEP, tetracycline resistant *N.gonorrhoeae* was higher in the doxycycline-PEP arm (38%) than at baseline (27%) and in the standard of care (SOC) arm (12%). [3] Additionally, although *S. aureus* carriage was lower in the doxycycline-PEP arm, a higher proportion had doxycycline resistance (16%) compared to SOC (8%). [3] In DOXYVAC, there was more high-level tetracycline resistance among incident gonorrhoea infections with resistance in the doxycycline-PEP arm (33.3%) compared to SOC (18.9%). [4]

Beyond standard microbiological approaches, including in the doxycycline-PEP/PrEP RCTs, there are limited data on genetic determinants of AMR in MSM. A study using residual rectal swab samples from MSM attending SHS in London estimated prevalence of the *mphA* gene (conferring azithromycin resistance) at 32.5%, and higher still (41.3%) among MSM with a diagnosed bacterial STI in the preceding 12 months. [19]

Microbiomes

The impact of sexual behaviour and HIV on the gastrointestinal and oropharyngeal microbiota is of increasing interest. [20-22] Several studies identified differences in the gut microbiota between MSM and men who exclusively have sex with women, and sexual

behaviour and antibiotic exposure (given differences in STI risk, testing, and treatment) are important potential confounders when studying microbiomes in MSM and people living with HIV.[18] It has also been suggested that both macrolides and tetracyclines have greater impacts on gastrointestinal microbiota compared to other antibiotics.[19] Moreover, alterations in gastrointestinal microbiome have been associated with metabolic, mental health and autoimmune diseases.[23,24] An oropharyngeal microbiome study noted that prevalence of select AMR genes ('resistome') was lower in the general population compared to MSM (ratio 0.41(0.26-0.65)), but found no difference when comparing MSM with and without recent antibiotic exposure.[25] This small cross-sectional study did not assess antibiotic STI prophylaxis and was limited by the lack of data on sexual behaviour including oral sex and ano-oral sexual contact.[25] Microbiome disturbances are multifactorial and differences in the gastrointestinal and oropharyngeal microbiota require careful interpretation as findings may be confounded by sexual behaviour and living with HIV.[22,27] Despite this, a systematic review of human gut resistome studies included no discussion on the potential impact of sexual behaviour or HIV. [26]

While the evidence of STI prophylaxis efficacy in MSM is compelling, given the lack of data on AMR, global differences in baseline AMR, and the potential addition of long-term antibiotic prophylaxis as a recommended STI prevention strategy in MSM, further research is required in the UK on the risks associated with STI prophylaxis and methods for monitoring and mitigation, such as enhanced surveillance. This research will provide data to fill important evidence gaps and develop the methodologies for further AMR research and optimised surveillance.

3 AIM AND OBJECTIVES

Research Question

What are the risks of AMR and microbiome impacts of antibiotic prophylaxis for sexually transmitted infections (STI prophylaxis) in MSM, and how can we evaluate and mitigate these risks?

Aim

To evaluate AMR and microbiome changes through bacterial genomics, and generate UK-based evidence to inform clinical and public health decisions on STI prophylaxis, future AMR research, and AMR surveillance.

3.1 Primary Objective

To assess feasibility and acceptability of detecting AMR emergence and microbiome changes in the gastrointestinal tract and oropharynx of MSM who use antibiotic STI prophylaxis through bacterial genomics.

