4 STUDY DESIGN & METHODS OF DATA COLLECTION

4.1 Study Design

Study design: Molecular epidemiology cohort study

Study site: Central and North West London (CNWL) NHS Foundation Trust Sexual Health Services (SHS). CNWL is one of the largest SHS in London, providing HIV PrEP to ~300 MSM each month, and routine care for ~3,000 MSM living with HIV.

Study population: MSM aged \geq 18 years. Target of 108 participants, with minimum 40 participants living with HIV¹, distributed evenly across three antibiotic exposure groups at enrolment:

- Group A (n=36): recent² and recurrent³ doxycycline STI prophylaxis use.
- Group B (n=36): recent² history of STI treatment with doxycycline.
- Group C (n=36): no recent² use of any antibiotic for any indication.

¹ 40 study places will be ring-fenced for MSM living with HIV, split evenly across the three groups (12-13 per group).

² recent is defined as within last 3 months.

³ recurrent is defined as 2 or more doses taken.

Eligible individuals meeting the criteria for group A and B, will be allocated to group A.

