9.2 Bioinformatic Analysis

The bioinformatic methodology and analysis is summarised here. The bioinformatic analysis will be fully outlined in a bioinformatic analysis plan (BAP). The BAP will be written by [name] (Chief Investigator) and [name] (Co-Investigator & Bioinformatician).

Bacterial taxonomic profiling will use both de novo assembly and read-mapping approaches. De novo assembly tools (e.g., MEGAHIT, metaSPAdes) will allow evaluation of taxonomy and AMR genetic diversity. Supervised binning methods will group assembled contigs (DNA sequences) by species using tools such as metaBAT, and the PubMLST/metaMLST reference databases which hosts assembled whole genome sequence data from over 480,000 bacterial isolates. Antibiotic resistance databases (e.g., Comprehensive Antibiotic Resistance Database) will be used to identify genes conferring resistance to tetracyclines (e.g., *tet(M)*, *tet(W)*, *tet(Q)*) and other important antibiotic classes (e.g., Macrolides *mphA*, *ermF*).

To mitigate potential assembly problems from low-abundance organisms, read mapping approaches will be undertaken using the pipeline CCMetagen which uses the National Centre for Biotechnology Information (NCBI) database as reference. Computationally intensive analyses will be carried out in a single *in silico* system that archives and integrates bacterial metagenomes and AMR genes with other rich metadata, and can organise and share genomes to allow integrated analyses and modelling.

Genome-wide association study analyses incorporating machine learning will identify core and accessory genome AMR elements (including plasmids) from complex samples. Genomic variation identified will include gene presence and absence; gene orthologs/alleles; insertions/deletions and single nucleotide polymorphisms (SNPs). These will be linked to AMR and other metadata.

Bacterial genera diversity (microbiome profiles) and AMR genes/gene mutations of interest ('resistome' profiles) will be compared between baseline study groups, and over time by use of doxycycline prophylaxis. Exploratory analysis of microbiome profiles by other characteristics including HIV status and sexual history will be undertaken.

This study does not analyse human DNA.

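### No Group A participant has a pre-exposure sample, so a flat course from Visit 1 to Visit 3 cannot be told apart from AMR emergence before Visit 1, and the analyses over time do not set new starters apart

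*Protocol*

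**What the plan says.** The study title concerns emergence of resistance. The primary objective in Protocol 3.1 reads: "To assess feasibility and acceptability of detecting AMR emergence and microbiome changes". It applies to the gut and throat of men who take STI prophylaxis, and it is a feasibility objective and not an effect estimate.

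Protocol 4.1 defines the exposed group as "Group A (n=36): recent² and recurrent³ doxycycline STI prophylaxis use". The footnotes add "recent is defined as within last 3 months" and "recurrent is defined as 2 or more doses taken". The other groups are "Group B (n=36): recent² history of STI treatment with doxycycline" and Group C (n=36), men without any antibiotic in the previous 3 months. Section 4.4 places all study procedures after eligibility and consent, and Section 5 sets visits at days 0, 180 and 360.

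Section 9.1 plans a descriptive analysis of AMR detection over time inside each enrolment group, with GEE logistic regression if there is enough within-person variation. Section 9.2 says that microbiome and resistome profiles "will be compared between baseline study groups, and over time by use of doxycycline prophylaxis". Emergence is not defined in either section.

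**The concern.** Emergence means a move from a state without the resistance determinant to a state with it, under exposure. A group recruited as prevalent users is first sampled after exposure has begun. Whatever was selected by the early doses is already present at Visit 1. What follows can show persistence, loss, or further acquisition in men still negative for a given gene, but not the change from an unexposed state.

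Two things are at stake. First, a stable Group A has two opposite explanations that its own data cannot separate. Second, men in Groups B or C who begin prophylaxis after Visit 1 could supply the before-and-after contrast, yet no analysis isolates them. In 9.1 they stay mixed with the non-starters of their enrolment group. In 9.2 the classification is by use, without a distinction between long-standing and new use. The study is also meant to develop methods for later AMR research and surveillance (3.2, objective F), so an unclear measure of emergence would carry forward.

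**Working it through.** **1. The plan's own figures (4.3).** With p = 0.325, the half-width is 1.96 × √(p(1 − p)/n).
- n = 108: 8.83 points (stated 8.85).
- n = 36: 15.3 points (stated 15.5).
- The exact binomial probability of at least 6 cases in 36 is 0.990 (stated 99%).

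These reproduce to within rounding. The point rests on the enrolment definitions and not on these figures. According to Section 2, the 32.5% is the prevalence of *mphA*, an azithromycin-resistance gene, in residual rectal swabs. The protocol gives no prevalence for the tetracycline genes.

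**2. Pre-exposure samples in Group A.** Entry requires at least 2 doses (4.1), the first sample follows entry (4.4, 5), and no earlier or archived sample is planned. The number of pre-exposure samples is 0 of 36.

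**3. What a flat course can mean.** Assume a pre-exposure prevalence of 32.5% and a true prevalence under use of 45% to 70%. If a share f of the rise occurred before Visit 1, the visible change is (1 − f) × (prevalence under use − 32.5%).
- f = 1: visible change 0, although the true rise is 12.5 to 37.5 points.
- f = 0.8: visible change 0.2 × 12.5 = 2.5 to 0.2 × 37.5 = 7.5 points.

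For scale, a single-visit prevalence in 36 men carries ±15.3 points. The precision of a paired change depends on within-person correlation, which is not given.

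**4. Men still able to show new detection of a gene.** 36 × (1 − Visit 1 prevalence):
- 32.5%: 24.3
- 60% (assumed): 14.4
- 80% (assumed): 7.2

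**5. What the baseline comparison of A with C can recover.** Power at 36 v 36, two-sided 5%, with Group C at 32.5% and assumed prevalence in Group A:

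| Group A | Power |
|---|---|
| 45% | 19% |
| 50% | 32% |
| 60% | 65% |
| 70% | 91% |

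Section 2 itself names sexual behaviour, antibiotic exposure and HIV as possible confounders.

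**6. Possible starters.** If 5% to 30% of the 72 men in B and C began prophylaxis (assumed), there would be 72 × 0.05 = 3.6 to 72 × 0.30 = 21.6, or about 4 to 22.

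**7. Dilution if starters and continuing users were combined.** Combined change = (n_cont × d_cont + n_start × d_start)/(n_cont + n_start). Assume n_cont = 36, d_cont = 0 and d_start = 20 points.
- 4 starters: 80/40 = 2.0 points
- 10 starters: 200/46 = 4.3 points
- 22 starters: 440/58 = 7.6 points

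**8. Is Visit 1 in B and C free of earlier prophylaxis?** Not by definition. Group C excludes only antibiotic use in the last 3 months, so a man who used prophylaxis before that qualifies. A Group B starter may have a pre-prophylaxis sample, but it follows recent doxycycline treatment.

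**The case against.** The strongest reply is that this is a descriptive feasibility cohort. The objective is to learn whether emergence can be detected, the GEE analysis is conditional and exploratory, and Section 2 already urges caution in interpreting microbiome differences. Group C and the baseline comparison address change accumulated before Visit 1. At the only documented prevalence, about 24 of 36 Group A men could still show new detection of a gene, and a man positive for one determinant can acquire others. Definitions and subsets can also be left to the SAP and the bioinformatic analysis plan.

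Much of this stands, and it rules out several stronger readings that a reader might infer:
- *That a flat Group A course will be reported as no emergence.* No section says so.
- *That 9.2 merges starters with continuing users.* It does not say that either. It fails to separate them, and 9.1 keeps Group A apart from B and C.
- *That the protocol expects participants to start.* Section 2 says that "implementation by the NHS in the UK is planned", but as a reason why AMR data are needed. No number of starters is planned.
- *That date of first use is not collected.* Section 4.4 lists prophylaxis use as a questionnaire topic at each visit. The items are not shown, so absence cannot be claimed.

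The core remains. Whether emergence can be detected depends on whether the design can observe it, and no later plan can create a pre-exposure sample for Group A. The protection from Group C is weak for moderate differences (step 5) and open to confounding.

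**Conclusion.** The point holds in a limited form. By design, 0 of 36 Group A men have a pre-exposure baseline, and this needs no assumption. It follows that a flat course in Group A is indistinguishable from emergence before Visit 1, and that the analyses as stated do not isolate the only men who could show change from a pre-prophylaxis state.

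The size of any dilution is illustrative. It depends on combining the two kinds of user, which the protocol does not state, and on assumed values for the number of starters, their rise and the absence of change in continuing users. Over the range shown, a 20-point rise would appear as 2.0 to 7.6 points. The sample size is unaffected. The change should be made because it improves what the study can say about its title question at little cost.

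**What to change.** In Protocol 9.1 and 9.2:
1. Define emergence per gene as absent at Visit 1 and detected later, with men negative for that gene at Visit 1 as the denominator.
2. Report the by-use comparison separately for (i) starters, with no prophylaxis before Visit 1 and use reported at Visit 2 or 3, showing those from Group B apart from those from Group C; and (ii) continuing Group A users, as persistence, loss or further acquisition, by time since first use.
3. State that a stable Group A is not evidence against emergence, and that the baseline comparison of A with C addresses earlier change only with limited precision and possible confounding.

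In 4.4, confirm that the Visit 1 questionnaire captures any earlier prophylaxis use and the date of first use, and add the item if it does not.

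The cost is analysis wording and at most a questionnaire item, with no extra participants, visits or samples. The downside is that the starter set may be small and support description only.

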3.2 Secondary Objectives

- A) To assess feasibility and acceptability of recruiting STI prophylaxis users via sexual health clinics versus online and obtaining appropriate samples.
- B) To evaluate the use of shotgun metagenomic sequencing to identify AMR genes or gene mutations conferring resistance to tetracycline and other relevant antibiotic classes.
- C) To evaluate the use of shotgun metagenomic sequencing to identify bacteria present in the gastrointestinal tract and oropharynx of MSM.
- D) To estimate the prevalence of AMR genes/gene mutations of interest and describe changes over time in the gastrointestinal tract and oropharynx of MSM using and not using STI prophylaxis.
- E) To characterise the gastrointestinal and oropharyngeal microbiomes and describe changes over time in MSM using and not using STI prophylaxis.
- F) To develop the methodology for future AMR research and surveillance in MSM and other relevant population groups.

